9.4 TREATMENTS

During the OLTP, all eligible patients will receive open-label IV rapastinel (450 mg) typically weekly or biweekly but the interval may be up to 4 weeks at the investigator’s discretion.

9.4.1 Treatments Administered

IP will only be administered to eligible patients by a medically qualified person as per the local and/or state regulations. The range of persons who can administer an IV can be a physician, a physician assistant, nurse, or nurse practitioner, etc, depending on the local and/or state law.

The IP will be administered using the provided prefilled syringes in a “slow bolus” injection to an upper extremity vein within approximately 1 to 2 minutes.

During IP administration and until completion of postadministration evaluation, a licensed physician must be immediately available and in close proximity to the patient(s) to attend to medical emergencies. The facility must have the capabilities, in accordance with the country and/or local regulations/standard of care, to resuscitate a patient in the event of a medical emergency.

At IP administration visits, the patient should not be released from the study center until a physician licensed in the country, state, or other local regulatory authority (investigator or subinvestigator) determines that they are medically able to leave the study center and provides written signoff not less than 15 minutes following administration.

9.4.2 Identity of Investigational Products

Rapastinel 450-mg IV Prefilled Syringes:

[REDACTED]

[REDACTED]

The prefilled syringe will be labeled with the treatment protocol number and kit number. The study center personnel will write the PID number on the prefilled syringe associated with the kit mentioned above. The prefilled syringe label will not have a tear-off portion and will remain on the prefilled syringe.

9.4.3 Handling of Investigational Products

The IP must be stored in a secure area and administered only to patients entered into the clinical treatment protocol, at no cost to the patient, in accordance with the conditions specified in this protocol.

[REDACTED] Study centers must report any temperature excursions as described in the Treatment Protocol Reference Manual or contact the sponsor or its designee for further instructions.

At the end of the treatment protocol, all IP must be accounted for. In addition, at the end of the treatment protocol, all unused IP should be returned to the sponsor or the local distributor at the address provided in the Treatment Protocol Reference Manual.

9.4.4 Method of Assigning Patients to Treatment Groups

After a patient signs the consent form at Visit 1, study center personnel will register the patient in the IWRS. [REDACTED]

This PID number will be used to identify the patient throughout the treatment protocol (ie, at all periods of the treatment protocol).

The IP will be labeled with medication kit numbers. The IWRS will provide the study center with the specific medication kit number(s) for each patient at each administration. Study centers will dispense IP according to the IWRS instructions. Study centers will also log on to the IWRS at subsequent visits to obtain an IP kit number for dispensing the IP. Study centers will receive the IWRS confirmation notifications for each transaction. All notifications are to be maintained with the treatment protocol source documents.

9.4.5 Selection of Dosages in the Treatment Protocol

The doses of rapastinel in this treatment protocol were selected based on two Phase 2 clinical studies in patients with MDD, in which single IV doses of rapastinel 5 mg/kg and 10 mg/kg were shown to produce marked antidepressant effects within 1 day that lasted approximately 1 week or longer in responding patients.

A 450-mg IV unit dose is expected to be appropriate for most patients, as this represents a dose of 4.5 mg/kg in a 100-kg patient and a dose of 9 mg/kg in a 50-kg patient.

9.4.6 Selection and Timing of Dose for Each Patient

9.4.6.1 Open-label Treatment Period

The IP will be administered IV using the assigned single-use prefilled syringes weekly, biweekly, or at intervals up to 4 weeks apart based on the discretion of the investigator. A patient may be switched between treatment frequencies at any time during the OLTP based on clinical presentation and the investigator's discretion.

9.4.7 Blinding

Not applicable

9.4.8 Unblinding

Not applicable

9.4.9 Prior and Concomitant Therapy

Patients should continue any non-IP MDD treatment regimen that was in place upon completion of the lead-in study (including any background ADT treatment for those who were in lead-in studies of the IP as an adjunctive therapy). Patients who require an alteration of MDD treatment regimen at any point during participation (including but not limited to addition of new therapeutic agent, increase in dose of any background ADT therapy the patient may be taking) due to an inadequate therapeutic response based on the judgment of the investigator should be withdrawn from participation.

Investigators should consult the lead-in study protocol from which each patient entered as a source of guidance regarding any other medications/treatments. Therapy considered necessary for the patient's welfare may be given at the discretion of the investigator.

Medication history (psychotropic medication history and all other medications during the past 12 months [to the extent feasible]) will be recorded in the lead-in study in the eCRF. Thereafter, any changes in concomitant medications or any new medications added will be recorded in the eCRF.

9.4.10 Other Restrictions

9.4.10.1 *Participation in Clinical Trials*

Patients may not participate in any other interventional clinical trial while taking part in this treatment protocol.

9.4.10.2 *Alcohol*

It is recommended that patients abstain from alcohol consumption during participation.

9.4.10.3 *Contraception*

For purposes of this protocol, females will be considered of childbearing potential unless they are naturally postmenopausal or permanently sterilized (ie, hysterectomy). Natural menopause is defined as the permanent cessation of menstrual periods, determined retrospectively after a woman has experienced 12 months of amenorrhea without any other obvious pathological or physiological cause.

For women of childbearing potential and male partners of women of childbearing potential who may participate in the treatment protocol, the following methods of contraception, if properly used, are generally considered reliable: hormonal contraceptives (ie, oral, patch, injection, implant), male condom with intravaginal spermicide, diaphragm or cervical cap with spermicide, vaginal contraceptive ring, intrauterine device [IUD], surgical sterilization (bilateral tubal ligation, bilateral salpingectomy), implantable permanent birth control device (ie Essure; note: device must be in place at least 3 months and completed confirmation test), vasectomized partner, or complete abstinence for the duration of the treatment protocol (periodic abstinence [such as calendar, ovulation, symptothermal, post-ovulation methods] and withdrawal are not acceptable methods of contraception).

Note: In Germany, the Czech Republic, and other local regions as applicable, acceptable methods of contraception include complete abstinence; single barrier (diaphragm or condom) combined with the use of IUD or contraceptive (oral, implantable, or injectable); or double barrier (diaphragm with condom).

The investigator and each patient will determine the appropriate method of contraception for the patient during the participation in the treatment protocol with consideration for local regulatory or IRB/EC requirements.

See Section 9.5.2.3 for pregnancy reporting procedures.

9.4.11 Monitoring Treatment Compliance

Not applicable

9.4.12 Treatment After Discontinuation

Patients whose MDD symptoms worsen or are determined by the investigator not to be adequately controlled prior to completing the OLTP should discontinue the treatment protocol and start appropriate treatment at the investigator's discretion. This new treatment will not be provided by the sponsor. Patients who initiate a new treatment for MDD must be discontinued from the treatment protocol.

9.5 EFFICACY AND SAFETY ASSESSMENTS

9.5.1 Diagnostic and Efficacy Assessments

Not applicable.

9.5.2 Safety Assessments

Provision for standard of care monitoring and procedures including those described below are the responsibility of the investigator and will not be provided by the sponsor. Patients must be evaluated by a physician or an appropriately trained health care professional at every visit and the evaluation must be documented. The procedures discussed below should be completed at each protocol visit.

9.5.2.1 Adverse Events

An AE is any untoward medical occurrence in a patient or clinical investigation patient administered a pharmaceutical product and which does not necessarily have to have a causal relationship with this treatment. An AE can therefore be any unfavorable and unintended sign (including an abnormal laboratory finding, for example), symptom, or disease temporally associated with the use of a medicinal product, whether or not considered related to the medicinal product (ICH-E2A).

For the purpose of the study center's data collection responsibilities, any untoward event that was reported from the time the patient signed the ICF until 30 days after the last known dose of IP (if the final visit does not occur) is to be considered an AE.

Examples of AEs are as follows:

- Changes in the general condition of the patient
- Subjective symptoms offered by or elicited from the patient
- Objective signs observed by the investigator or other study center personnel
- All diseases that occur after signing informed consent, including any change in severity or frequency of pre-existing disease
- All clinically relevant abnormalities in laboratory values or clinically relevant physical findings that occur during the treatment protocol

Please note that medical procedures scheduled prior to consenting, but occurring during the treatment protocol should not be captured as AEs, but should be listed in the medical history if related to a pre-existing condition.

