9.5.2.1.4 Reporting Adverse Events and Serious Adverse Events

At each visit, patients are to be queried regarding any AEs or SAEs that have occurred since the previous visit. Patients will be asked to volunteer information with a nonleading question such as, “How do you feel since your last visit?” Study center personnel will record all pertinent information in the patient’s eCRF.

All AEs must be recorded on the appropriate AE reporting page of the patient’s eCRF whether or not they are considered causally related to the IP.

For every AE, the investigator must:

- Provide an assessment of the seriousness of the event (ie, is it an SAE?), as well as the severity and casual relationship
- Document all actions taken with regard to the IP
- Detail any other treatment measures taken for the AE
- Document the outcome of the AE

In addition, patients are to be reminded, as described in the ICF and in accordance with Section 9.5.2.1, to notify study center personnel of any AEs occurring during the 30-day posttreatment protocol period. Any AEs reported by the patient (or patient representative) during this period are to be recorded in original source documents. AEs are also to be recorded in the eCRF if at least one of the following conditions is met: 1) the event meets the criteria for an SAE (see Sections 9.5.2.1.3 and 9.5.2.1.4), and/or 2) the event is judged by the investigator to be potentially causally related to IP (Section 9.5.2.1.1).

Any AEs that are ongoing at the time of patient exit from the protocol will be followed until the condition returns to pre-treatment protocol status, has resolved or stabilized, or can be explained as being unrelated to the IP. If a follow-up visit is deemed necessary for appropriate safety surveillance, it will take place within 30 days of the last known dose of IP.

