9.5.2.2 Immediate Reporting of Serious Adverse Events

The sponsor is required to inform worldwide regulatory authorities of SAEs that meet specific criteria. Therefore, the sponsor must be notified immediately regarding any SAE that occurs after informed consent is obtained.

Within 24 hours of learning of any AE that meets one of the criteria for an SAE, the study center personnel must report the event to Global Drug Safety on the SAE Form for Clinical Trials. The Study Physician may also be notified by telephone.

If, during follow-up, any nonserious AE worsens and eventually meets the criteria for an SAE, that AE should be recorded as a new SAE.

The study center must transmit the SAE Form for Clinical Trials to the SAE email address or fax number shown below. Even if an initial report is made by telephone, the SAE Form for Clinical Trials completed with all available details must still be emailed or faxed within 24 hours of knowledge of the event at the study center.

Supplemental information should be submitted as soon as available and may include laboratory results, radiology reports, progress notes, hospital admission and emergency room notes, holding and observation notes, discharge summaries, autopsy reports, and death certificates.

The investigator is expected to take all therapeutic measures necessary for resolution of the SAE. Any medications or procedures necessary for treatment of the SAE must be recorded on the appropriate pages of the patient’s eCRF. All SAEs are to be followed by the study center staff until resolution or until the SAE is deemed stable. ***The sponsor may contact the study center to solicit additional information or follow up on the event.***

[Redacted]

[Redacted]

[Redacted]

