9.7.6.1 Adverse Events

AEs will be coded by system organ class (SOC) and preferred term using the *Medical Dictionary for Regulatory Activities*.

An AE (classified by preferred term) that occurs during the OLTP or thereafter will be considered a treatment-emergent adverse event (TEAE) if it was not present before the date of the first dose of IP in the OLTP or was present before the first dose of IP of the first lead-in study and increased in severity during the OLTP or thereafter. If more than 1 AE is reported before the date of the first dose of IP in the OLTP and coded to the same preferred term, the AE with the greatest severity will be used as the benchmark for comparison with the AEs occurring during the OLTP that were also coded to that preferred term.

The number and percentage of patients reporting TEAEs during the OLTP will be tabulated by SOC, preferred term, and further categorized by severity and causal relationship to the IP. If more than 1 AE is coded to the same preferred term for the same patient during the OLTP, the patient will be counted only once for that preferred term using the most severe and most related occurrence for the summarization by severity and by causal relationship to the IP.

The incidence of common ($\geq 2\%$ of patients) TEAEs during the OLTP will be summarized by preferred term and will be sorted by decreasing frequency.

An SAE that occurred between the date of the first dose of the IP and 30 days after the date of the last dose of IP, inclusive, will be considered an on-therapy SAE. The number and percentage of patients who had on-therapy SAEs during the OLTP will be summarized by preferred term and sorted by decreasing frequency.

The number and percentage of patients who had fatal on-therapy SAEs during the OLTP will be summarized by preferred term and sorted by decreasing frequency.

The incidence of TEAEs leading to premature discontinuation of IP during the OLTP will be summarized by preferred term and will be sorted by decreasing frequency.

Listings will be presented for all patients with SAEs, patients with AEs leading to discontinuation, and patients who died (if any).

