11.1 ADVERSE EVENTS

AEs will be coded using the *Medical Dictionary for Regulatory Activities (MedDRA)*.

An AE (classified by preferred term) that occurs during the OLTP will be considered a treatment-emergent adverse event (TEAE) if it was not present before the date of the first dose of IP in the OLTP or was present before the first dose of IP of the first lead-in study and increased in severity during the OLTP. If more than 1 AE is reported before the date of the first dose of IP in the OLTP and coded to the same preferred term, the AE with the greatest severity will be used as the benchmark for comparison with the AEs occurring during the OLTP that were also coded to that preferred term. An AE that occurred more than 30 days after the date of the last dose of open-label IP will not be counted as a TEAE. An AE that becomes serious during the OLTP will also be considered as TEAE.

The incidence of common (in $\geq 2\%$ of participants) TEAEs during the OLTP will be summarized by preferred term and will be sorted by decreasing frequency.

An SAE that occurred between the date of the first dose of the open-label IP and 30 days after the date of the last dose of IP, inclusive, will be considered a treatment-emergent SAE (TESAE).

The incidence of death, TEAE, treatment-related TEAE, TESAE, TEAEs leading to premature discontinuation of IP during the OLTP will be summarized.

Listings will be presented for all participants with SAEs, participants with AEs leading to discontinuation, and participants who died (if any).

12.0 **HEALTH ECONOMICS AND OUTCOMES ANALYSES**

Not applicable.

13.0 **INTERIM ANALYSIS**

No interim analysis is planned for this treatment protocol.

14.0 **DETERMINATION OF SAMPLE SIZE**

Not applicable.

15.0 **COMPUTER METHODS**

Statistical analyses will be performed using [REDACTED]

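### After exit, nonserious AEs judged unrelated may stay out of the eCRF, although the TEAE count appears to run to 30 days after the last dose

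*Protocol*

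**What the plan says.** **Collection.** Protocol 9.5.2.1 treats as an AE any untoward event reported from consent "until 30 days after the last known dose of IP (if the final visit does not occur".

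**Database entry.** Protocol 9.5.2.1.4 begins with a general rule: AEs go on the eCRF "whether or not they are considered causally related to the IP". It then gives a specific rule for the time after treatment. Patients are to be reminded, "in accordance with Section 9.5.2.1, to notify study center personnel of any AEs occurring during the 30-day posttreatment protocol period". Reports in that period go into source documents, and "AEs are also to be recorded in the eCRF if at least one of the following conditions is met": the event is serious, or the investigator judges it potentially related. Protocol 9.5.2.2 separately covers serious events: "the sponsor must be notified immediately regarding any SAE that occurs after informed consent is obtained".

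**Counting.** Under protocol 9.7.6.1, an AE "that occurs during the OLTP or thereafter will be considered a treatment-emergent adverse event (TEAE", subject to a comparison with what was present before. SAP 11.1 opens its definition with the open-label period only and then adds a limit: "An AE that occurred more than 30 days after the date of the last dose of open-label IP will not be counted" as a TEAE. That limit carries no condition on seriousness or causality. SAP 17.0 lists the changes from the protocol analyses, and a change to the TEAE window is not among them.

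**Output.** AEs are the only safety parameter (protocol 9.7.6, SAP 11.0). SAP 11.1 reports overall incidences of death, TEAEs, treatment-related TEAEs, treatment-emergent SAEs and TEAEs leading to discontinuation. By preferred term it tabulates only TEAEs in at least 2% of participants.

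**The concern.** The rule for what enters the database after treatment is narrower than the rule for what counts as a TEAE. An analysis can count only what was entered. If the counting window runs to 30 days after the last dose, one class of event inside it can be missing by design: new, nonserious AEs judged unrelated and reported after exit.

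What is at stake is the completeness of the overall TEAE incidence and of the only by-term TEAE table. The filter also rests on an unblinded causality judgement. Protocol 9.5.2.1.1 allows a negative answer when the event is likely due to underlying disease or is common in the population, and nonserious symptoms after stopping treatment in MDD patients could readily be classed that way. SAP 16.6 is cautious in the other direction and assigns a causal relationship when the assessment is missing, but it cannot do so for an event that was never entered.

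**Working it through.** The documents state no figure on this point, so there is none to reproduce. The check compares the rules and then measures the span of days.

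**Step 1: does the general eCRF rule override the specific one?** If every AE still had to go on the eCRF in the posttreatment period, the two conditions (serious, potentially related) would do nothing. The specific rule must therefore narrow the general one for that period.

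**Step 2: do days 1 to 30 after the last dose count for TEAEs?** This is an inference, for four reasons.
- SAP 11.1 says during the open-label period, but then sets an upper limit of 30 days after the last dose.
- Visits are at most 4 weeks apart (protocol 9.1.1), and 4 × 7 = 28 < 30. For a patient on schedule, a limit at 30 days would exclude almost nothing unless events after the open-label period are in scope.
- Protocol 9.7.6.1 extends the definition beyond the open-label period, and SAP 17.0 records no departure from it.
- The same protocol section defines on-therapy SAEs out to 30 days after the last dose, yet summarises them as occurring during the open-label period. The phrase is thus used loosely enough to include those days.

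**Step 3: which events fall between the rules?** After exit and by day 30:
- Serious: eCRF entry required, so no gap.
- Nonserious, potentially related: eCRF entry required, so no gap.
- Nonserious, judged unrelated: source documents only, yet not excluded by SAP 11.1. This is the gap.

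**Step 4: how many days?** Let *f* be the days from last dose to exit (an assumption, since the schedule in protocol 9.5.5 is redacted). The filtered part of the TEAE window is 30 − *f*.
- Last dose given at the exit visit: 30 − 0 = 30 days
- Exit undosed at the next weekly visit: 30 − 7 = 23 days
- Exit undosed at the next biweekly visit: 30 − 14 = 16 days
- Exit undosed at the next 4-weekly visit: 30 − 28 = 2 days
- Exit at a visit on day 30: 30 − 30 = 0 days

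**Step 5: scale of the by-term table.** If all of the approximately 1800 planned patients are treated (assumption), the threshold is 0.02 × 1800 = 36 patients. A term with 36 true cases would leave the table if one were not entered, since 35/1800 = 1.94%. This shows how the threshold works; it does not estimate an effect.

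**Step 6: would moving the start of the posttreatment period to the last dose be a safe repair?** No. The natural reading of that period is 30 days from leaving the protocol, although the cross-reference to 9.5.2.1 leaves some doubt. On that reading, for a patient who exits undosed on day 28, potentially related AEs are now captured to day 28 + 30 = 58. Restarting the period at the last dose would end capture at day 30 and lose 58 − 30 = 28 days.

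**The case against.** The strongest counter-argument is that the TEAE window is inferred. The SAP sentence only excludes events beyond day 30; it does not say that all earlier events count. Its opening words, and the heading of the common-TEAE summary, confine TEAEs to the open-label period. The limit could also serve a patient who stays in the protocol undosed. On that strict reading, an unrelated nonserious AE after exit is outside the outputs and nothing is lost. This cannot be ruled out, but it is the weaker reading for the reasons in step 2. If it is what the sponsor intends, the SAP departs from the protocol definition without listing the change, so SAP 11.1 still needs a clarifying sentence.

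It is also fair to say that the two-condition eCRF rule looks deliberate, that the aim of the protocol is continued access, and that the events concerned are the least consequential ones. All of that stands and keeps the point minor.

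Three stronger readings are tempting but not supported.
- A reader might infer from the parenthesis in protocol 9.5.2.1 that patients without a final visit have these AEs entered while others do not. The eCRF rule in 9.5.2.1.4 makes no exception for such patients, and what counts as a final visit depends on redacted text.
- A reader might infer that safety signals in general are lost. Serious and potentially related AEs are required in the eCRF.
- A reader might see a fault in the timing of the follow-up visit ("it will take place within 30 days of the last known dose of IP"). That visit is optional, and AEs ongoing at exit are followed in any case until resolved, stable or explained.

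**Conclusion.** The mismatch holds, as a minor point. On the better reading of SAP 11.1 with protocol 9.7.6.1, overall TEAE incidence and the by-term table can be somewhat understated for new nonserious AEs judged unrelated after exit. The direction is known only if those events are meant to count. The span is 0 to 30 days per patient, depending on when exit falls. The effect on reported percentages cannot be estimated, because the documents give no AE rates and the schedule is redacted. Deaths, SAEs and potentially related TEAEs are unaffected. Nothing here supports a claim of material bias in the safety conclusions.

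**What to change.** 1. Protocol 9.5.2.1: delete the parenthesis that ties the 30-day limit to the absence of a final visit.
2. Protocol 9.5.2.1.4: require eCRF entry of all AEs reported up to 30 days after the last dose. For any later days in the posttreatment period, keep the present reporting of SAEs and potentially related AEs. Do not move the start of that period or shorten it.
3. SAP 11.1: state that TEAEs are counted through 30 days after the last dose of open-label IP.

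The cost is wording in two protocol sections and one SAP sentence, plus some extra eCRF entries for nonserious AEs judged unrelated. Sites must already write down these reported events in source documents, so the added work is mainly data entry.
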